# 6.3 Visit Windows

Follow-up visits are scheduled every two months after randomization during the first year and every three months during the second year. Each participant will have a visit calendar generated at the time of randomization and they will be encouraged to complete visits within 1 week before or after the scheduled date. However, it is likely that some visits will not be completed within this window. To maximize the amount of on-trial information available from each participant, we will define visit windows as (a) first year after randomization: from two weeks before to six weeks after a scheduled visit; and (b) second year after randomization: from one month before to two months after a scheduled visit. Visits that do not occur within these windows will be deemed missed.

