## **1.3 Overall Design and Study Interventions**

BetaFat is a two arm, unblinded study in which volunteers with prediabetes or drug-naïve, recent onset, mild type 2 diabetes will be randomized to: (1) metformin or (2) gastric banding. The study will recruit patients over a 27-month period and follow each individual for a total of 24 months on study intervention. The primary outcomes will be  $\beta$ -cell compensation for insulin resistance, measured in two ways as defined below. The anticipated duration of the BetaFat study is five years, including pre-trial preparation and post-trial analysis and reporting.

ß-cell function,  $\alpha$ -cell function, insulin sensitivity and glucose tolerance will be assessed using intravenous and oral tests. Both intravenous and oral tests will be obtained at baseline and after 12 and 24 months of therapy. Use of oral and intravenous tests will allow us to examine different aspects of  $\beta$ -cell function. Such use will also allow us to examine how well relatively simple measures of  $\beta$ -cell function,  $\alpha$ -cell function and insulin sensitivity (i.e., from fasting samples and oral glucose tolerance tests) correlate to more sophisticated measures (i.e., from glucose clamp studies) in the prediction of  $\beta$ -cell decline and/or response to treatment. Finally, a series of adipokines/inflammatory markers will be measured to determine whether they predict changes in  $\beta$ - and  $\alpha$ -cell function, insulin sensitivity and glucose tolerance without and with therapy.

Clinically, the project will serve as a test of concept for use of gastric banding relatively early in the spectrum of obesity and  $\beta$ -cell disease. We will derive information on the extent of weight loss necessary to fully arrest or reverse the  $\beta$ -cell disease, as well as potential clinical markers for successful treatment. Biologically, the results will provide crucial information on potential mediators of  $\beta$ -cell failure and its arrest or reversal in the context of obesity. Those mediators will guide the development of more effective strategies for prevention and early treatment of T2D with the aim of arresting or reversing the progressive  $\beta$ -cell disease.

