intensify messaging about the importance of participation and identify reasons for drop-outs, targeting them for retention efforts; (b) we may increase overall enrollment if the difference between real and projected drop-outs is small (budgets limit large increases in enrollment); (c) we will examine projected completion in relation to power, noting that our current 80% power threshold is below the projected effect size, so that we may be able to tolerate some excess loss to follow-up; (d) if dropouts are occurring after 12 months, we may consider changing the primary outcomes to rates of change in the two primary beta cell measures, as we have used in prior observational studies with different durations of follow-up. Note that we plan to assess main outcomes at 12 and 24 months on treatment, allowing this approach.

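### Do visit windows counted from randomisation conflict with clamps counted from treatment start?

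*Combined protocol and SAP*

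**What the plan says.** Section 6.3 runs on randomisation. "Each participant will have a visit calendar generated at the time of randomization", and staff work to a target: "they will be encouraged to complete visits within 1 week before or after the scheduled date". Wider limits then decide whether a visit counts as attended:

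- "first year after randomization: from two weeks before to six weeks after a scheduled visit"
- "second year after randomization: from one month before to two months after a scheduled visit"

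The section closes: "Visits that do not occur within these windows will be deemed missed".

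Most other places count from treatment. Section 1.3 will "follow each individual for a total of 24 months on study intervention" and says: "Both intravenous and oral tests will be obtained at baseline and after 12 and 24 months of therapy". Section 5.4 repeats that "we plan to assess main outcomes at 12 and 24 months on treatment". Sections 6.2.2 and 6.2.3 date the OGTTs and clamps from the start of metformin or the band operation. Section 6.2 defines study end as 24 months from that same point, or treatment failure by HbA1c if earlier. Section 9.2 ties its 12- and 24-month comparisons to the start of the interventions.

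Section 4.5 supplies the gap between the clocks. Metformin begins the day after the second baseline visit. Band surgery has a two-week goal, with no upper limit.

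**The concern.** One visit is dated by two clocks that no sentence connects. In the metformin arm they differ by about a day. In the band arm they differ by the wait for surgery, and the pre-operative work-up in section 3.4.2 (psychological, cardiac, anaesthetic) takes place after randomisation. If surgery were late enough, a clamp done on exactly its section 6.2.3 date would be labelled missed under section 6.3, and essentially only in the band arm.

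There is a second strand. Read literally, section 6.2 gives no 24-month study end to someone who never starts the assigned treatment, although section 9 analyses everyone as randomised.

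At stake would be the co-primary endpoints of an unblinded trial. If late-operated or never-operated band participants dropped out of the analysis, the comparison would no longer be fully randomised and some power would be lost.

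**Working it through.** **Inputs.** Late window limits from section 6.3: six weeks = 42 days in year 1; two months = 2 × 30.44 = 60.9 days in year 2. Planned start delay D after randomisation from section 4.5: 1 day (metformin), 14 days (band goal). Encouraged lateness limit L from section 6.3: 7 days. The 12-month visit is taken as the last first-year visit, which fits the two-monthly schedule; section 6.3 does not say so.

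**Formula.** A clamp on its section 6.2.3 date falls D days after the calendar date in section 6.3. A clamp L days late falls D + L days after it. Days to spare = late limit − D − L. The early limits never bind because D is not negative.

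| Case | 12-month | 24-month |
|---|---|---|
| Metformin, on date | 42 − 1 = 41 | 60.9 − 1 = 59.9 |
| Metformin, a week late | 42 − 1 − 7 = 34 | 60.9 − 1 − 7 = 52.9 |
| Band at goal, on date | 42 − 14 = 28 | 60.9 − 14 = 46.9 |
| Band at goal, a week late | 42 − 14 − 7 = 21 | 60.9 − 14 − 7 = 39.9 |

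**Surgical delay at which the clocks conflict.** For a clamp on its date: more than 42 days at 12 months, or about 61 days at 24 months. For a clamp a week late: more than 42 − 7 = 35 days, or 60.9 − 7 = 53.9 days. If the 12-month visit took the second-year window, its threshold would also be about 61 days. The primary analysis uses baseline and study end (section 3.2), so about 61 days is the threshold that matters most, more than four times the goal (60.9 / 14 = 4.4).

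**Which clock staff use.** At the goal the two 24-month dates differ by 14 days out of 24 × 30.44 = 730.6 days, or 1.9% of follow-up.

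**What the missed label does.** No sentence removes the data from a visit so labelled. Section 9 uses all available data by assigned arm. Section 6.3 gives its reason for the wide windows as keeping as much on-trial information as possible. Section 5.3 treats attendance as an adherence measure, which is a natural use for the label. If follow-up length differs between arms, section 9.5 (Handling of Missing Data) switches the outcome to rate of change.

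**Never-starters.** Section 6.3 gives every participant a calendar. The schedule in section 6.2 puts a clamp at 24 months with no exception by treatment received. Section 3.4.2, on the HbA1c safety endpoint, speaks of end-of-study visits as scheduled for 24 months. Together these give a never-starter a final clamp visit.

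**Size if data were dropped anyway.** Suppose one never-operated participant were omitted and would have had none of the 0.99 SD effect projected in section 9.3. The band mean would rise by 0.99 / 44 = 0.0225 to 0.99 / 35 = 0.0283 SD, which is 2.8% to 3.5% of the projected 0.80 difference. This does not apply to late-operated participants, who do receive the band.

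**Power.** Completers: 44 × 0.9² = 35.6, so about 35 per group. A noncentral t calculation with 35 per group gives 80.1% at 0.68; with ANCOVA at correlation 0.5 (SD × √(1 − 0.25)) it gives 89.9% at 0.68 and 80.2% at 0.59, against the stated 80%, 89% and 80%. Losing 2, 4 or 7 of the 35 band-arm clamps would lower the last figure to 79.0%, 77.7% or 75.3%. Those counts are assumptions for illustration; nothing in the documents predicts them.

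**The case for a change.** The strongest case for a change is that the ambiguity falls on one arm, concerns the date rule for the co-primary endpoints, and would be settled by people who know the allocation. The operation has a goal but no limit, and the work-up that could delay or cancel it comes after randomisation. Even at the two-week goal, the section 6.2.3 date lies outside the one-week target in section 6.3, so two coordinators could book different days. Section 9.5 deals with early HbA1c endpoints and unequal follow-up time, but not with out-of-window clamps or never-starters. A sentence or two would settle it at little cost.

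Much of this stands as description: the two clocks are there, section 6.2 is silent on never-starters, and the frequency of long delays is unknown. The reference in section 3.4.2 is also imperfect support, since it concerns the HbA1c endpoint, names no clock and cites a table number that differs from the one in section 6.2.

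The step from description to harm does not stand. Bias requires a completed clamp to be thrown out, or a scheduled 24-month clamp not to be done. The protocol instructs neither, and its general analysis rule points the other way. Missing the one-week target has no stated consequence, because that target is only encouragement.

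**Conclusion.** This is a minor wording inconsistency that an analyst would resolve sensibly: keep every completed clamp with its actual date, and treat the 24-month calendar visit as study end for anyone who never started treatment. Followed as written, the plan gives sound results. At the planned delays all clamps are in window, with at least 21 days to spare at 12 months and about 40 at 24 months even when a band clamp is a week late. For a clamp on its date, conflict begins only at a surgical delay of more than 42 days (12-month) or about 61 days (24-month). The stated power and sample size do not change.

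The conclusion rests on three assumptions: that the 12-month visit takes the first-year window (otherwise its threshold is longer), that the missed label records attendance and does not exclude data, and that surgery usually happens near the two-week goal. The documents give no distribution of surgical delay, so the last cannot be tested. If it failed, the second, which agrees with section 9, would still keep completed clamps in the analysis. A cross-reference between sections 6.2.3 and 6.3 would be tidier, but no gain in the validity or precision of the primary comparison has been shown.

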# **7** SAFETY / HUMAN SUBJECTS PROTECTION

This study will be conducted in compliance with the protocol and all applicable regulatory requirements. The participating sites have Federal-wide Assurance with the Office for Human Research Protections and they follow local HIPAA regulations. Prior to study initiation, the

protocol and the informed consent documents will be reviewed and approved by the IRB at each participating site and by an independent Data and Safety Monitoring Board (DSMB). Any amendments to the protocol or consent materials must be approved by the DSMB and the IRBs before implementation.

# 7.1 Data and Safety Monitoring Board (DSMB)

A DSMB consisting of appropriately qualified and conflict-free independent experts is appointed by the National Institute of Diabetes and Digestive and Kidney Diseases (NIDDK) and provides input to the Institute. Board members are chosen by the NIDDK without consultation with the study investigators. The purpose of the Board is to assure independent review as to whether study participants are exposed to any unreasonable risk because of study participation, and to monitor study progress and integrity. In addition to safety monitoring, the Board can review unblinded study data and make recommendations for early termination of studies for achieving an end point or for futility. Before any of the studies in the RISE Consortium can begin, the DSMB, in addition to the local IRBs, must approve the protocol. Any subsequent major changes to the protocol must also be approved by the DSMB and IRBs.

Following each DSMB meeting a summary of AEs and DSMB recommendations is provided to the IRB of each participating clinical center and other institutional monitoring committees/boards as needed.

# 7.2 Data and Safety Monitoring Plan

## 7.2.1 Informed Consent

The informed consent process will be conducted by qualified study personnel. All participants must read, sign and date a consent form prior to participation in any stage of the study. The informed consent will be revised and participants re-consented whenever there is new, clinically significant information regarding the safety of the interventions, when a relevant protocol amendment is approved, or when any new information becomes available that may affect an individual's participation in the study.

## 7.2.2 Safety Review Plan and Monitoring

- A. Justification of Sample Size: See Section 9.3.
- B. *Stopping Rules*: The DSMB may suggest terminating a study arm at any time for safety or efficacy reasons. Details of interim analysis plans and stopping rules can be found in Sections 9.4 and 9.5.

- C. *Safety Monitoring Committee*: The RISE Consortium will appoint an internal Safety Monitoring Committee which review AEs or other safety-related problems sent to them from the field. The RISE SMC will review AEs in a blinded manner. An external Safety Review Officer will evaluate any serious adverse events (SAE) where the SMC is not in agreement about whether the event is related to study drug as well as certain specified SAEs of concern (e.g., pancreatitis). The Safety Review Officer will not be blinded to study intervention.
- D. *Safety Review Plan*: The DSMB will meet twice yearly to review study progress and safety as described in Section 7.1.

## 7.2.3 Confidentiality

- A. *Protection of Participant Privacy*: Participants' names are linked to study IDs only on a single recruitment database and only certified project personnel are authorized to have access to this database. Only study IDs will be used in all other study databases (e.g., for tracking and merging and sharing with other sites and the NIH). NIH has obtained a certificate of confidentiality for the entire RISE Consortium, including the BetaFat Study
- B. *Database Protection*: All hard-copy files are stored in locked cabinets within locked offices at the clinical centers. Primary electronic data are entered into and maintained on a secure USC server with two-level password protection against non-project personnel. The server is backed up daily and automatically. Data for analyses common to other studies in the RISE Consortium will be transmitted to a secure, password-protected website maintained by the RISE Coordinating Center (CoC) at George Washington University. The CoC holds no personal identifiers and stores the data on its enterprise server accessible only by approved staff.

At the end of the study, all hard copy records will be kept in a secure locale for a period dictated by local IRB and Institutional policies, as well as FDA, regulations, whichever is longest.

C. *Confidentiality during AE Reporting*: AEs and SAEs are recorded on data collection forms and reported to the Coordinating Center without personal identifiers. Identifiers on accompanying documents (such as medical records) are removed before submission to the Coordinating Center and any subsequent transfer to the Safety Monitoring Committee and/or Safety Review Officer.

# 7.3 Expected Side Effects

The BetaFat Study will use two interventions: (a) metformin or (b) gastric banding with the LapBand system. The expected side effects are provided below.

#### 7.3.1 Metformin

Known adverse effects associated with metformin are primarily gastrointestinal (diarrhea, nausea, vomiting, abdominal bloating, flatulence, anorexia), hematologic (reduced vitamin B12 levels and, rarely, megaloblastic anemia), and the rare possibility of lactic acidosis. The risk of lactic acidosis associated with metformin use will be minimized by (1) monitoring liver transaminases, (2) monitoring renal function, and (3) temporary discontinuation of metformin before radiologic studies involving the injection of contrast dye, surgical procedures requiring reduced fluid intake, and serious illness that might be associated with hypoxia, dehydration, or shock. To monitor for clinically significant vitamin B12 deficiency, we will follow guidelines in the metformin package insert and perform a complete blood count annually while participants are taking metformin.

#### 7.3.2 Gastric Band

A variety of risks have been reported in the literature in association with gastric banding: erosion into stomach (2-9%), slippage (2-18%), leakage (1-4%), tubing or port malfunctions (1-10%), infection (1-5%), bleeding (<1%) and dyspepsia/ulceration (5-20%), and death (<0.1%). In [name] program at USC, there have been no deaths, erosions or perforations in nearly 400 operations (~200 with diabetes). The rate of slippage, leak or malfunction requiring revision is <3%.

## 7.4 Risk Management

#### 7.4.1 Metformin

To minimize the risk of gastrointestinal side effects, metformin is given with meals, started at a dose of 500 mg/d, and titrated to the target does of 1000 mg bid over a four-week period. If GI side effects develop and are mild, the patient is encouraged to remain on the study medication. If GI side effects are moderate or difficult to tolerate, metformin is reduced to the next lowest dose (for example, 1000 mg bid to 1000 mg + 500 mg; 1000 mg + 500 mg to 500 mg bid; etc.). If symptoms persist, metformin is reduced to the next step. If GI symptoms resolve, metformin is re-escalated by 500 mg per day each week until reaching the previously tolerated dose. The participant will continue on the maximum tolerated dose.

Renal insufficiency increases the risk of lactic acidosis associated with metformin. To asses renal insufficiency, serum creatinine and estimated GFR (eGFR) will be calculated using the CKD-Epi equation (ref . Ann Intern Med. 2009;150(9):604-612.) at screening and every six months on therapy. Participants must have an eGFR of 45 mL/minute/1.73 m^2 or higher to be eligible for the BetaFat study. . Metformin will be discontinued if eGFR is below 30 mL/minute/1.73 m^2. If eGFR  $\geq$ 30 and <45 mL/minute/1.73 m^2 then the RISE Safety Committee will review the case to assess the benefits and risks of continuing treatment, and make a recommendation to the clinical center investigators about whether to continue the participant on metformin.

Metformin will be discontinued temporarily 24 hours before, during, and for 48 hours after any of the following events: 1) procedure involving the injection of contrast dye; 2) surgery or other procedure requiring general anesthesia; 3) any illness that could be associated with hypoxia, circulatory failure, or dehydration; 4) hospitalization. Serum creatinine will be rechecked no sooner than 48 hours after the conclusion of the event and study medication recommenced if appropriate.

To monitor for clinically significant vitamin B12 deficiency, we will follow guidelines in the metformin package insert and perform a complete blood count annually while participants are taking metformin.

#### 7.4.2 Gastric Band

Risks of the banding procedure will be minimized by (a) exclusion of people with standard clinical contraindications to the device (see list in the Appendix), (b) use of a single surgeon with an experienced surgical team and state-of-the art facilities; (c) pre-operative participant education and evaluation and careful post-operative care by a multidisciplinary team experienced in medical, surgical, nutritional and psychological aspects of bariatric surgery; (d) availability of an on-call physician to address symptoms and patient concerns; and (e) availability of the surgical team and an experienced radiologist to diagnose and treat potential complications.

#### 7.4.3 DEXA Scans

Potentially fertile women have a urine pregnancy test immediately prior to DEXA, which is performed only if the pregnancy test is negative.

#### 7.4.4 MRI Scans

Individuals with contraindications to MRI will be excluded from the study during Screening and enrollment. As an additional safety measure, all enrolled participants go through a safety

screening with the on-site MRI technician on the day of the exam to ensure that they are "MRI Safe". The scanner operates within FDA guidelines, particularly for RF power deposition (SAR) and gradient switching speed (dB/dt). During the exam, participants have intercom access to the operating technician. An emergency "squeeze ball" is also available to immediately stop the exam. The MRI procedure will be terminated immediately at the subject's wish. Participants will be informed that failure to complete the experiment will not result in any form of prejudice, or affect access to medical care.

#### 7.4.5 Other indications for Interruption of Discontinuation of Medication

- A. *Pregnancy:* Study medications will not be administered if a participant becomes pregnant. The participant is referred to a high risk obstetrics clinic for further care.
- B. *Lactation:* No study medication will be administered to women who are nursing a baby.
- C. *Lactic acidosis:* Any study participant who experiences a bout of lactic acidosis will have metformin permanently discontinued.
- D. *Dermatological problems:* Any study participant who experiences severe dermatological problems, such as urticaria, bullous rashes, exfoliative dermatitis, Stevens-Johnson syndrome, thought to be related to study medication will have study medication permanently discontinued.

#### 7.4.6 Hyperglycemia

Participants are instructed regarding the signs and symptoms of hyperglycemia and are to call the clinic with any concerns. HbA1C will be measured at six-month intervals. If a value exceeds 7%, therapy is invigorated by frequent telephone contact and/or visits to encourage optimal medication adherence and lifestyle choices. If a scheduled HbA1C exceeds 8.0% the test will be repeated one month later. If the value remains >8.0%, end-of study testing is performed and the participant completes participation in the study and is referred for standard care of diabetes.

#### 7.4.7 Glucose and Arginine Infusions

Irritation of a vein resulting in phlebitis can occur with administration of concentrated glucose solutions. The risk will be decreased by minimizing the use of concentrated solutions and selecting large veins for infusion of solutions. Overdose of arginine can be fatal, especially in children. We will use a dose of 5 gm. in adults. This dose has been used safely in many studies.

